#### Acute Adverse Events

Adverse events occurring in the time period from the signing of the informed consent, through 90 days post treatment will be considered acute adverse events.

#### Late Adverse Events (as applicable)

Adverse events occurring in the time period from the end of acute monitoring, to 5 years post treatment, will be defined as late adverse events. Immune-mediated adverse events such as adrenal insufficiency, hypothyroidism/thyroiditis, hyperthyroidism, hypophysitis, diabetes mellitus, nephritis and renal dysfunction will be monitored by medical oncology and other specialists during follow up visit whereas radiation side effects will be monitored by radiation oncology.

#### Severity

Adverse events will be graded by a numerical score according to the defined NCI Common Terminology Criteria for Adverse Events (NCI CTCAE) Version 5.0. Adverse events not specifically defined in the NCI CTCAE will be scored on the Adverse Event log according to the general guidelines provided by the NCI CTCAE and as outlined below.

- Grade 1: Mild
- Grade 2: Moderate
- Grade 3: Severe or medically significant but not immediately life threatening
- Grade 4: Life threatening consequences
- Grade 5: Death related to the adverse event

#### Serious Adverse Events

ICH Guideline E2A and the UTSW IRB define serious adverse events as those events, occurring at any dose, which meets any of the following criteria:

- Results in death
- Immediately life-threatening
- Results in inpatient hospitalization or prolongation of existing hospitalization
- Results in persistent or significant disability/incapacity
- Results in a congenital anomaly/birth defect
- Based upon appropriate medical judgment, may jeopardize the subject's health and may require medical or surgical intervention to prevent one of the other outcomes listed in this definition.

Note: A "Serious adverse event" is by definition an event that meets *any* of the above criteria. Serious adverse events may or may not be related to the research project. A serious adverse event determination does not require the event to be related to the research. That is, both events completely unrelated to the condition under study and events that are expected in the context of the condition under study may be serious adverse events, independent of relatedness to the study itself. As examples, a car accident requiring  $\geq$ 24 hour inpatient admission to the hospital would be a serious adverse event for any research participant; likewise, in a study investigating end-stage cancer care, any hospitalization or death which occurs during the protocol-specified period of monitoring for adverse and serious adverse events would be a serious adverse event, even if the event observed is a primary clinical endpoint of the study.

Pre-planned hospitalizations or elective surgeries are not considered SAEs. Note: If events occur during a pre-planned hospitalization or surgery, that prolong the existing hospitalization, those events should be evaluated and/or reported as SAEs.

 NCI defines hospitalization for expedited AE reporting purposes as an inpatient hospital stay equal to or greater than 24 hours. Hospitalization is used as an indicator of the seriousness of the adverse event and should only be used for situations where the AE truly fits this definition and NOT for hospitalizations associated with less serious events. For example: a hospital visit where a patient is admitted for observation or minor treatment (e.g. hydration) and released in less than 24 hours. Furthermore, hospitalization for pharmacokinetic sampling is not an AE and therefore is not to be reported either as a routine AE or in an expedited report.

#### **7.2.2** Unanticipated Problems Involving Risks to Subjects or Others (UPIRSOs):

The phrase "unanticipated problems involving risks to subjects or others" is found, but not defined in the HHS regulations at 45 CFR 46, and the FDA regulations at 21 CFR 56.108(b)(1) and 21 CFR 312.66. For device studies, part 812 uses the term unanticipated adverse device effect, which is defined in 21 CFR 812.3(s). Guidance from the regulatory agencies considers unanticipated problems to include any incident, experience, or outcome that meets ALL three (3) of the following criteria:

Unexpected in terms of nature, severity or frequency given (a) the research procedures
that are described in the protocol-related documents, such as the IRB-approved research
protocol and informed consent document; and (b) the characteristics of the subject
population being studied;

#### AND

Related or possibly related to participation in the research (possibly related means there is
a reasonable possibility that the incident, experience, or outcome may have been caused
by the procedures involved in the research);

#### AND

 Suggests that the research places subjects or others at greater risk of harm (including physical, psychological, economic, or social harm) than was previously known or recognized. Note: According to OHRP, if the adverse event is serious, it would always suggest a greater risk of harm.

#### Follow-up

All adverse events will be followed up according to good medical practices.

# 7.3 Steps to Determine If a Serious Adverse Event Requires Expedited Reporting to the SCCC DSMC and/or HRPP

Step 1: Identify the type of adverse event using the NCI Common Terminology Criteria for Adverse Events (CTCAE v5).

Step 2: Grade the adverse event using the NCI CTCAE v5.

Step 3: Determine whether the adverse event is related to the protocol therapy. Attribution categories are as follows:

- Definite The AE is clearly related to the study treatment.
- Probable The AE is likely related to the study treatment.
- Possible The AE may be related to the study treatment.
- Unlikely The AE may NOT be related to the study treatment.
- Unrelated The AE *is clearly NOT related* to the study treatment.

Note: This includes all events that occur within 30 days of the last dose of protocol treatment. Any event that occurs more than 30 days after the last dose of treatment and is attributed (possibly, probably, or definitely) to the agent(s) must also be reported as indicated in the sections below.

Step 4: Determine the prior experience of the adverse event. Expected events are those that have been previously identified as resulting from administration of the treatment. An adverse event is considered unexpected, for expedited reporting purposes only, when either the type of event or the severity of the event is not listed in:

- the current known adverse events listed in the Agent Information Section of this protocol (if applicable);
- the drug package insert (if applicable);
- the current Investigator's Brochure (if applicable)
- the Study Agent(s)/Therapy(ies) Background and Associated Known Toxicities section of this protocol

# 7.3.1 Reporting SAEs and UPIRSOs to the Simmons Comprehensive Cancer Center (SCCC) Data Safety Monitoring Committee (DSMC)

All SAE/UPIRSOs at all sites, which occur in research subjects on protocols for which the SCCC is the DSMC of record require reporting to the DSMC regardless of whether IRB reporting is required. All SAEs/UPIRSOs occurring during the protocol-specified monitoring period should be submitted to the SCCC DSMC within 5 business days of the PI or delegated study team members awareness of the event(s). In addition, for participating centers other than UTSW, local IRB guidance should be followed for local reporting of serious adverse events.

The UTSW Radiation Oncology research office is responsible for submitting SAEs/UPIRSOs to the SCCC DSMC Coordinator and AstraZeneca. Hardcopies or electronic versions of the eIRB Reportable Event report; FDA Form #3500A forms, or other sponsor forms, if applicable; and/or any other supporting documentation available should be submitted to the DSMC Coordinator. The DSMC Coordinator forwards the information onto the DSMC Chairman who determines if immediate action is required. Follow-up eIRB reports, and all subsequent SAE/UPIRSO documentation that is available are also submitted to the DSMC Chair who determines if further action is required.

Written reports to:

Department of Radiation Oncology Clinical Research Office The University of Texas Southwestern Medical Center

[contact]

UTSW SCCC Data Safety Monitoring Committee Coordinator

Email: [contact] [contact] or deliver to BLB.306

UTSW Institutional Review Board (IRB)

Submit a Reportable Event via eIRB with a copy of the final sponsor report as attached supporting documentation

Reporting Unanticipated Problems Involving Risks to Subjects or Others (UPIRSOs) to the UTSW HRPP/IRB

UTSW reportable event guidance applies to all research conducted by or on behalf of UT Southwestern, its affiliates, and investigators, sites, or institutions relying on the UT Southwestern IRB. Additional reporting requirements apply for research relying on a non-UT Southwestern IRB.

According to UTSW HRPP/IRB policy, UPIRSOs are incidents, experiences, outcomes, etc. that meet ALL three (3) of the following criteria:

- 1. Unexpected in nature, frequency, or severity (i.e., generally not expected in a subject's underlying condition or not expected as a risk of the study; therefore, not included in the investigator's brochure, protocol, or informed consent document),AND
- 2. Probably or definitely related to participation in the research, AND
- Suggests that the research places subjects or others at a greater risk of harm (including physical, psychological, economic, or social harm) than was previously known or recognized. Note: According to OHRP, if the adverse event is serious, it would always suggest a greater risk of harm.

For purposes of this policy, UPIRSOs include unanticipated adverse device effects (UADEs) and death or serious injury related to a humanitarian use device (HUD).

UPIRSOs must be promptly reported to the UTSW IRB within 5 working days of PI awareness.

For research relying on a non-UT Southwestern IRB (external, central, or single IRB):

Investigators relying on an external IRB who are conducting research on behalf of UT Southwestern or its affiliates are responsible for submitting **LOCAL** UPIRSOs to the UT Southwestern IRB within 5 working days of PI awareness. Investigators must report to their relying IRB according to the relying IRB's policy. In addition, the external IRB's responses or determinations on these local events must be submitted to the UT Southwestern IRB within 10 working days of receipt.

#### Events NOT meeting UPIRSO criteria:

Events that do NOT meet UPIRSO criteria should be tracked, evaluated, summarized, and submitted to the UTSW HRPP/IRB at continuing review.

For more information on UTSW HRPP/IRB reportable event policy, see https://www.utsouthwestern.edu/research/research-administration/irb/assets/policies-combined.pdf.

#### 7.3.2 Reporting SAEs and UPIRSOs to AstraZeneca

#### Reporting of serious adverse events

All SAEs will be reported, whether or not considered causally related to the investigational product, or to the study procedure(s). The reporting period for SAEs is the period immediately following the time that written informed consent is obtained through 90 days after the last dose of durvalumab or until the initiation of alternative anticancer therapy. The investigator and/or Sponsor are responsible for informing the Ethics Committee and/or the Regulatory Authority of the SAE as per local requirements.

The investigator and/or sponsor must inform the FDA, via a MedWatch/AdEERs form, of any serious or unexpected adverse events that occur in accordance with the reporting obligations of 21 CFR 312.32, and will concurrently forward all such reports to AstraZeneca. A copy of the MedWatch/AdEERs report must be emailed to AstraZeneca at the time the event is reported to the FDA. It is the responsibility of the sponsor to compile

all necessary information and ensure that the FDA receives a report according to the FDA reporting requirement timelines and to ensure that these reports are also submitted to AstraZeneca at the same time.

- \* A cover page should accompany the MedWatch/AdEERs form indicating the following:
- "Notification from an Investigator Sponsored Study"
- The investigator IND number assigned by the FDA
- The investigator's name and address
- The trial name/title and AstraZeneca ISS reference number (ESR-##-#####)
- \* Sponsor must also indicate, either in the SAE report or the cover page, the causality of events in relation to all study medications and if the SAE is related to disease progression, as determined by the principal investigator.
- \* Send SAE report and accompanying cover page by way of email to AstraZeneca's designated mailbox: **[contact]**

If a non-serious AE becomes serious, this and other relevant follow-up information must also be provided to AstraZeneca and the FDA.

Serious adverse events that do not require expedited reporting to the FDA still need to be reported to AstraZeneca preferably using the MedDRA coding language for serious adverse events. This information should be reported on a monthly basis and under no circumstance less frequently than quarterly. In the case of blinded trials, AstraZeneca will request that the Sponsor either provide a copy of the randomization code/ code break information or unblind those SAEs which require expedited reporting.

#### Reporting of deaths to AstraZeneca

All deaths that occur during the study, or within the protocol defined 90 day post last dose of durvalumab safety follow up period must be reported to AstraZeneca as follows:

- Death that is clearly the result of disease progression should be documented but should not be reported as an SAE.
- Where death is not due (or not clearly due) to progression of the disease under study, the AE causing the death must be reported to AstraZeneca as a SAE within 24 hours. The report should contain a comment regarding the co involvement of progression of disease, if appropriate, and should assign main and contributory causes of death.
- Deaths with an unknown cause should always be reported as a SAE.

Deaths that occur following the protocol-defined 90-day post-last-dose of durvalumab safety follow-up period will be documented <<as events for survival analysis>>, but will not be reported as an SAE. However, if an investigator learns of any SAEs, including death, at any time after the patient has been permanently withdrawn from study, and he/she considers there is a reasonable possibility that the event is related to study treatment, the investigator should notify the study sponsor and AstraZeneca/MedImmune Drug Safety.

#### **Medication errors**

Medication errors are not regarded as AEs but AEs may occur as a consequence of the medication error. If a medication error occurs in the course of the study, then the Investigator or other site personnel informs Sponsor within 1 day i.e., immediately but no later than 24 hours of when he or she becomes aware of it. The Sponsor works with the Investigator to ensure that all relevant information is completed within 1 or 5 calendar days. The Sponsor must report to AstraZeneca Patient Safety using the designated Safety e-mailbox

#### **Overdose**

An overdose is defined as a patient receiving a dose of durvalumab in excess of that specified in the Investigator's Brochure, unless otherwise specified in this protocol.

Any overdose of a study patient with durvalumab, with or without associated AEs/SAEs, is required to be reported within 24 hours of knowledge of the event to the sponsor and AstraZeneca/MedImmune Patient Safety or designee using the designated Safety emailbox within 7 calendar days or sooner when required. If the overdose results in an AE,

the AE must also be recorded as an AE. Overdose does not automatically make an AE serious, but if the consequences of the overdose are serious, for example death or hospitalization, the event is serious and must be recorded and reported as an SAE. There is currently no specific treatment in the event of an overdose of durvalumab. The investigator will use clinical judgment to treat any overdose.

# Other events requiring reporting Hepatic function abnormality

Hepatic function abnormality that fulfills the biochemical criteria of a potential Hy's Law case in a study patient, with or without associated clinical manifestations, is required to be reported as "hepatic function abnormal" within 24 hours of knowledge of the event to the sponsor and AstraZeneca Patient Safety using the designated Safety e-mailbox (see Section 10.3.2 for contact information), unless a definitive underlying diagnosis for the abnormality (e.g., cholelithiasis or bile duct obstruction) that is unrelated to investigational product has been confirmed. The criteria for a potential Hy's Law case is Aspartate Aminotransferase (AST) or Alanine Aminotransferase (ALT) ≥3x Upper Limit of Normal (ULN) together with Total Bilirubin (TBL) ≥2xULN at any point during the study following the start of study medication irrespective of an increase in Alkaline Phosphatase (ALP).

- If the definitive underlying diagnosis for the abnormality has been established and is unrelated to investigational product, the decision to continue dosing of the study patient will be based on the clinical judgment of the investigator.
- If no definitive underlying diagnosis for the abnormality is established, dosing of the study patient must be interrupted immediately. Follow-up investigations and inquiries must be initiated by the investigational site without delay.

Each reported event of hepatic function abnormality will be followed by the investigator and evaluated by the sponsor and AstraZeneca/MedImmune.

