		investigator, in discussion with AstraZeneca Clinical Study Lead.  For patients treated with durvalumab in combination with tremelimumab or tremelimumab monotherapy:  A. Permanently discontinue tremelimumab for Grade 3 diarrhea/colitis. HOLD durvalumab until resolution to Grade ≤ 1; durvalumab alone can be resumed after completion of steroid taper (<10 mg prednisone per day or equivalent)  B. Permanently discontinue both durvalumab and tremelimumab for 1) Grade 4 diarrhea/colitis or 2) Any grade of intestinal perforation Grade 4 Permanently discontinue study drug/study regimen.	If perforation is suspected, consult a surgeon experienced in abdominal surgery immediately without any delay.
Hepatitis  Infliximab should not be used for management of immune-related hepatitis.  PLEASE SEE shaded area immediately below this	Any Grade (Refer to NCI CTCAE applicable version in study protocol for defining the CTCAE grade/severity)	General Guidance	For Any Grade     Patients should be thoroughly evaluated to rule out any alternative etiology (e.g., viral hepatitis, disease progression, concomitant medications).     Monitor and evaluate transaminases (aspartate aminotransferase [AST], alanine aminotransferase [ALT], alkaline phosphatase [ALP]) and total bilirubin.
section to find guidance for management of "Hepatitis (elevated LFTS)" in hepatocellular carcinoma	ALT or AST ≤ 3 x ULN or total bilirubin ≤1.5 x ULN	No dose modifications.     If it worsens, then consider holding therapy.	Continue transaminase and total bilirubin monitoring per protocol.
secondary tumour involvement of the liver with abnormal baseline values [BLV])	ALT or AST > 3 ≤ 5 x ULN or total bilirubin > 1.5 ≤ 3 x ULN	Hold study drug/study regimen dose until ALT or AST ≤ 3 x ULN or total bilirubin ≤ 1.5 x ULN. Resume study drug/study regimen after completion of steroid taper (<10 mg prednisone or equivalent).  Permanently discontinue study drug/study regimen for any case meeting Hy's law laboratory criteria (AST or ALT >3 × ULN AND	total bilirubin (e.g., every 1 to 2 days) unti- transaminases and total bilirubin elevations improve or resolve.

		bilirubin ≥2 × ULN without initial findings of cholestasis (i.e., elevated ALP) and in the absence of any alternative cause.	If event is persistent (>2 to 3 days) or worsens, promptly start prednisone 1 to 2 mg/kg/day PO or IV equivalent.

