	ALT or AST > 5- ≤ 10 x ULN	Hold study drug/study regimen. Resume study drug/study regimen if elevations downgrade to ALT or AST ≤ 3 x ULN or total bilimbin ≤ 1.5 x ULN after completion of steroid taper (<10 mg prednisone, or equivalent).      If in combination with tremelimumab, do not restart tremelimumab.	Promptly initiate empiric IV methylprednisolone at 1 to 2 mg/kg/day or equivalent.     Check CPK and aldolase (to rule out myositis)     Perform Hepatology Consult, abdominal workup, and imaging as appropriate.     If still no improvement within 2 to 3 days despite 1 to 2 mg/kg/day methylprednisolone IV or equivalent, promptly start treatment with an additional immunosuppressant (e.g., mycophenolate mofetil 0.5 – 1 g every 12 hours then taper in consultation with hepatology consult or relevant practice guidelines). Discuss with Clinical Study Lead if mycophenolate is not available. Infliximab should NOT be used.
	Concurrent ALT or AST > 3 x ULN and total bilirubin > 2 x ULN  ALT or AST > 10 x ULN OR total bilirubin > 3 x ULN	Permanently discontinue study drug/study regimen.	- Promptly initiate empiric IV methylprednisolone at 1 to 2 mg/kg/day or equivalent If still no improvement within 2 to 3 days despite 1 to 2 mg/kg/day methylprednisolone IV or equivalent, promptly start treatment with an additional immunosuppressant (e.g., mycophenolate mofetil 0.5 – 1 g every 12 hours then taper in consultation with hepatology consult or relevant practice guidelines). Discuss with Clinical Study Lead if mycophenolate is not available. Infliximab should NOT be used.  - Perform Hepatology Consult, abdominal workup, and imaging as appropriate.
Hepatitis  (elevated transaminases and total bilirubin)  Infliximab should not be used for management of immune-related hepatitis.	Any Elevations of AST, ALT, or T. Bili as Described Below	General Guidance	For Any Elevations Described  - Patients should be thoroughly evaluated to rule out any alternative etiology (e.g., viral hepatitis, disease progression, concomitant medications, worsening of liver cirrhosis [e.g., portal vein thrombosis]).  - Monitor and evaluate AST, ALT, ALP, and T. Bili.  - For hepatitis B (HBV) + patients: evaluate quantitative HBV viral load, quantitative Hepatitis B surface antigen (HBsAg), or Hepatitis B envelope antigen (HBeAg).

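### With no diagnosis established, ALT or AST above 3x ULN with bilirubin above 2x ULN meets inconsistent dosing instructions in section 7.3.2 and two rows of the Appendix I hepatitis table

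*Combined protocol and SAP*

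**What the plan says.** Three places address the same liver-test pattern.

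- **Section 7.3.2, hepatic function abnormality.** A potential Hy's Law case is "Aspartate Aminotransferase (AST) or Alanine Aminotransferase (ALT) ≥3x Upper Limit of Normal (ULN) together with Total Bilirubin (TBL) ≥2xULN", whatever the ALP. If a definitive diagnosis "has been established and is unrelated to investigational product", then "the decision to continue dosing of the study patient will be based on the clinical judgment of the investigator". Otherwise: "If no definitive underlying diagnosis for the abnormality is established, dosing of the study patient must be interrupted immediately", and follow-up investigations must start without delay. The paragraph does not mention permanent discontinuation and does not refer to Appendix I.
- **Appendix I, hepatitis table, row for ALT or AST above 3x and up to 5x ULN, or bilirubin above 1.5x and up to 3x ULN.** The basic instruction is to hold dosing until values fall, then resume after a steroid taper. A further sentence reads "Permanently discontinue study drug/study regimen for any case meeting Hy's law laboratory criteria". It defines these as AST or ALT above 3x with bilirubin at least 2x ULN, and limits them to cases "without initial findings of cholestasis (i.e., elevated ALP) and in the absence of any alternative cause".
- **Appendix I, hepatitis table, combined-elevation row.** The trigger is "Concurrent ALT or AST > 3 x ULN and total bilirubin > 2 x ULN" and the action is permanent discontinuation. The row has no condition on ALP or alternative cause.

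Three other statements bear on scope. Section 4.2 bases dosing decisions on the Appendix I algorithms. Section 7.2.1, on adverse events of special interest, limits those guidelines to events the investigator considers causally related. The general considerations in Appendix I apply immune-mediated management where no clear alternative etiology exists.

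**The concern.** The protocol itself singles this pattern out as a potential Hy's Law case and requires a report within 24 hours. An investigator facing it should find one dosing instruction. For the undiagnosed patient there are up to three, with no statement of how 7.3.2 and Appendix I rank against each other. Two investigators could treat identical results differently, each with a text to point to. The pattern concerns possible serious liver injury: section 7.1.2 lists hepatitis among the potentially fatal reactions to durvalumab.

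**Working it through.** No figure in the plan needs reproducing. The check compares the texts.

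**Step 1. Does one patient fall under all three texts?** Take ALT 4x and bilirubin 2.5x ULN.
- Section 7.3.2: 4 ≥ 3 and 2.5 ≥ 2, so it applies.
- Appendix I, 3x to 5x row: 3 < 4 ≤ 5 and 1.5 < 2.5 ≤ 3, so it applies. The numerical part of its Hy's law sentence is also met (4 > 3, 2.5 ≥ 2).
- Appendix I, combined-elevation row: 4 > 3 and 2.5 > 2, so it applies.

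**Step 2. What does each text instruct?**

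| Case | Section 7.3.2 | Appendix I, 3x to 5x row | Appendix I, combined-elevation row |
|---|---|---|---|
| A. No diagnosis, no cholestasis | Interrupt | Permanently discontinue | Permanently discontinue |
| B. No diagnosis, ALP raised | Interrupt | Hold, resume after taper | Permanently discontinue |
| C. Definitive unrelated cause | Investigator's judgement | Hy's law sentence does not apply | Permanently discontinue, if read alone |

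In case A both Appendix I rows agree, and 7.3.2 stops short of them. In case B Appendix I disagrees with itself, because ALP is an exclusion in one row and absent from the other. Case C is taken up with the counter-arguments below.

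**Step 3. Do the thresholds match?**

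| Text | ALT or AST | Bilirubin | Role of ALP |
|---|---|---|---|
| Section 7.3.2 | ≥ 3x | ≥ 2x | Disregarded |
| Appendix I, Hy's law sentence | > 3x | ≥ 2x | Raised ALP excludes |
| Appendix I, combined-elevation row | > 3x | > 2x | Not mentioned |

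ALT or AST at exactly 3x meets only 7.3.2. Bilirubin at exactly 2x, with ALT or AST above 3x, meets 7.3.2 and can meet the Hy's law sentence, but not the combined-elevation row.

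**Step 4. Could the combined-elevation row simply override the other?** The table does not say so. If it did, every patient with ALT or AST above 3x and bilirubin above 2x would be discontinued whatever the ALP. The Hy's law sentence would then add only the patient whose bilirubin is exactly 2x, and its two conditions would have almost no effect. The rule in section 4.2 about the greatest degree of toxicity compares organ systems; it does not rank rows within hepatitis.

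**Step 5. Frequency.** The documents do not give it. Section 1.3 reports hepatitis in 12% of 1889 durvalumab patients with various cancers, with Grades 3, 4 and 5 at 4.4%, 0.4% and 0.2%. Applied to 50 patients: 50 × 0.12 = 6 cases, and 50 × (0.044 + 0.004 + 0.002) = 2.5 of Grade 3 or worse. These count hepatitis of any kind, not the combined ALT-and-bilirubin pattern, so they are context and not an estimate.

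The shaded part of the hepatitis table, for hepatocellular carcinoma or liver involvement with abnormal baseline values, concerns another population and was left out.

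**The case against.** **Interruption is a first step.** An immediate stop pending work-up is compatible with later permanent discontinuation, so a site can obey both texts. This stands, and it makes case A the milder inconsistency. A reader might go further and infer that a site following 7.3.2 may restart durvalumab. The documents do not support that: 7.3.2 gives no resumption rule for the undiagnosed case. Resumption appears only in the 3x to 5x row of Appendix I.

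**A confirmed unrelated cause.** A reader might infer a second conflict for, say, a confirmed bile duct obstruction: the investigator's judgement under 7.3.2, permanent discontinuation under Appendix I. That does not hold. Section 7.2.1 confines the guidelines to events judged causally related, the general considerations in Appendix I apply where no clear alternative etiology exists, and the Hy's law sentence exempts alternative causes. Only the combined-elevation row, read in isolation, says otherwise. Moreover, 7.3.2 does not leave dosing to judgement for just any cause; the diagnosis must be definitive and unrelated to the product.

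**The protocol already names its dosing source.** Section 7.3.2 is a reporting section, section 4.2 sends dosing decisions to Appendix I, and the annex says management should follow it. This is a fair point about case A. It is weakened because Appendix I calls itself a recommendation, section 7.2.1 describes it as an aid to clinical judgement, and 7.3.2 imposes a mandatory instruction in the protocol body. It does not help in case B, where following Appendix I still leaves two different actions.

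**Conclusion.** The inconsistency is real for the patient with no definitive product-unrelated diagnosis. It is sharpest when ALP is raised, with three different instructions, two of them within Appendix I. Without cholestasis it is milder: 7.3.2 mentions interruption only, while both Appendix I rows require permanent discontinuation. The differing boundary signs are a smaller matter, confined to values exactly at 3x or 2x ULN. Where an unrelated cause is established, the most that remains is that the combined-elevation row does not repeat the exemption found elsewhere.

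The size cannot be stated as a number of patients, because no rate for the combined pattern is given. The sample size and the efficacy analyses in section 10 do not depend on it. The case for correction rests on the seriousness of the event and the low cost of the edit. The conclusion assumes that the Appendix I rows are read as written, with no order of priority between them; none is stated.

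**What to change.** The sponsor must reconcile the hepatic paragraph of section 7.3.2 with the two Appendix I hepatitis rows on:

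1. the thresholds, including whether the boundary values are in or out;
2. whether raised ALP changes the action;
3. whether an alternative cause changes the action, stated in the combined-elevation row as well;
4. the dosing consequence while no diagnosis is established, and once one is.

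The protocol body should then state which text governs, with a cross-reference from 7.3.2 to Appendix I. Because the annex is maintained as a standalone document, a sentence in the protocol body may be the practical route. The same edit can correct the pointer in 7.3.2 to section 10.3.2 for contact details, since 10.3.2 is the toxicity analysis. Which action applies is for the sponsor's clinicians; this review takes no position.

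The cost is a wording amendment with IRB approval, and agreement with the drug supplier on the annex. It adds no tests, visits or patients.
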